**Figure 1. Recruitment, Enrollment, and CHW Intervention Timeline**

Participant Projections	Year 2			Year 3			Year 4			Year 5			Cumulative enrollment for entire study				
	Apr - June 2018	July - Sept 2018	Oct - Dec 2018	Jan - Mar 2019	Apr - June 2019	July - Sept 2019	Oct - Dec 2019	Jan - Mar 2020	Apr - June 2020	July - Sept 2020	Oct - Dec 2020	Jan - Mar 2021	Apr - June 2021	July - Sept 2021	Oct - Dec 2021	Jan - Mar 2022	Enrollment by wave
Wave 1																	
PCP1	Recruit/ Enroll N=48		CHW intervention	CHW intervention													
PCP2	Recruit/ Enroll N=48		CHW intervention	CHW intervention													
PCP3	PCP Recruitment	Recruit/ Enroll N=48	CHW intervention	CHW intervention													336 out of 960 target participants = 35%
PCP4	PCP Recruitment	Recruit/ Enroll N=48	CHW intervention	CHW intervention													
PCP5	PCP Recruitment	Recruit/ Enroll N=48	CHW intervention	CHW intervention													
PCP6	PCP Recruitment	Recruit/ Enroll N=48	CHW intervention	CHW intervention													
PCP7	PCP Recruitment	Recruit/ Enroll N=48	CHW intervention	CHW intervention													
Wave 2																	
PCP8	Recruit/ Enroll N=48		CHW intervention	CHW intervention													
PCP9	Recruit/ Enroll N=48		CHW intervention	CHW intervention													
PCP10	Recruit/ Enroll N=48		CHW intervention	CHW intervention													288 out of 960 target participants = 30%
PCP11	Recruit/ Enroll N=48		CHW intervention	CHW intervention													
PCP12	Recruit/ Enroll N=48		CHW intervention	CHW intervention													
PCP13	Recruit/ Enroll N=48		CHW intervention	CHW intervention													
Wave 3																	
PCP14	Recruit/ Enroll N=48		CHW intervention	CHW intervention													
PCP15	Recruit/ Enroll N=48		CHW intervention	CHW intervention													
PCP16	Recruit/ Enroll N=48		CHW intervention	CHW intervention													36 out of 960 target participants = 35%
PCP17	Recruit/ Enroll N=48		CHW intervention	CHW intervention													
PCP18	Recruit/ Enroll N=48		CHW intervention	CHW intervention													
PCP19	Recruit/ Enroll N=48		CHW intervention	CHW intervention													
PCP20	Recruit/ Enroll N=48		CHW intervention	CHW intervention													

## C2. EHR-CHW Intervention

The implementation and content of EHR and CHW components of the intervention at each PCP align with the Chronic Care Model.

**EHR Components:** The EHR component of the integrated EHR-CHW intervention will include: 1) An alert to identify South Asian patients with elevated BMI ( $\geq 23 \text{ kg/m}^2$ ) and recommendation to PCPs to order an HbA1c test as part of standard of care; and 2) Generation of registry lists of individuals with A1C 5.7-6.4% (individuals with incident pre-diabetes). Building upon existing protocols the study team will coordinate the implementation of the proposed EHR modifications at each PCP. The implementation process will be characterized by: 1) Workflow analysis; 2) Procedures for identifying system requirements; and 3) Adequate training and support for users upon and following go-live.

Workflow analysis. Using a rapid assessment process, baseline workflow analysis will be conducted at each PCP. The workflow analysis consists of an iterative process including ethnographic observation and key informant interviews (see below) to provide contextual data on organizational workflow, culture, and practice. Results from the analysis will be used to improve alert and registry functions and to align with the workflow of each PCP.

Implementation of System Requirements for the Intervention. System requirement definition and implementation ensures that various EHR systems across PCPs are configured to provide the functionality called for by the study design. The research team will work with a PCIP specialist to develop a framework for creating the proposed EHR enhancements. This process includes specifying and confirming the system's functional requirements based on the users' needs as well as the study design. The EHR modifications will be made at each PCP, and providers and staff will be trained. Functional and technical specifications (and any updates) will be maintained and documented for training, workflow development, troubleshooting and dissemination purposes.

Training. The training will be designed to enable clinicians to use the decision-supports and/or alerts independently, proficiently, and effectively. At the start of the intervention period, clinicians will receive an estimated 8 hours of didactic and interactive training. Individualized training will also be available during the initial implementation period for all users. Clinic staff will also be provided with user documentation.

### **CHW Component:**

CHW Protocol. Patients that meet eligibility criteria will be drawn from registry lists and randomized to intervention or waitlisted control. Patients assigned to the intervention group will be sent an invitation letter to participate in the CHW intervention (See *Recruitment Letter for CHW Intervention*). Invitation letters will be followed up with phone calls by CHWs (See *Script for Telephone Screening for CHW Intervention*). In addition, a screening form (See *Telephone Screening Form for CHW Intervention*) will be completed to verify eligibility. CHWs will call patients a maximum of 10 times over a two-week period at varying times of day to invite them to enroll into the study. Patients assigned to the waitlisted control group will be recruited and contacted in the same manner as intervention participants except after completion of intervention rounds.

### *Consenting and data collection with Intervention participants*

Consent forms will be completed with intervention participants in an in-person meeting. Baseline surveys will also be conducted by NYU study staff with intervention participants within two weeks after consent. (See *CHW Participant Baseline Survey*). A CHW Participant Followup Survey will be completed with intervention participants approximately six months after the start of intervention in order to evaluate the effectiveness of the CHW intervention.

Participants enrolled during the COVID-19 pandemic will be asked questions on vaccine hesitancy and COVID19 vaccination; as well as questions on mental health and mobile/technology use in order to understand how participants' chronic conditions and mental health was affected in during the pandemic and to understand how best to tailor remote intervention strategies to encourage vaccination among patients with overweight and pre-diabetes who are at higher risk for complications from COVID-19.

The CHW intervention includes a protocol that consists of 5 monthly 90-minute group health education sessions, providing the tools and strategies to prevent diabetes. All sessions employ adult learning techniques and group-based learning and activities. All session materials have been culturally and linguistically adapted into Bengali, Urdu, Hindi, Punjabi, and Nepali. Sessions will be held in remotely via audio phone calls via telephone, MCIT NYU approved Webex and Zoom platform or in community spaces identified by partner agencies, and multiple sessions will be held weekly to accommodate patient's varying schedules. Links to the health education sessions will be created via NYU approved Webex and Zoom platforms that are provided for use across the institution. These NYU Webex and Zoom links will be shared to participants via text message through NYU MCIT secured phones(see Text Message Script). The study team has developed training materials on how to use the NYU Webex and Zoom platforms to provide to research participants. Use of the Zoom will be used solely for the purpose of delivering the health education materials and will not involve discussion of PHI. In order to maintain anonymity for Zoom, for each session, the study staff will create Zoom waiting rooms for participants to be renamed as "Participant 1, Participant 2, etc.) prior to individuals joining the larger session with other research participants.

In addition to these group sessions, patients will receive up to 9 follow-up phone calls from CHWs, during which individualized challenges, strategies, and action plans for improving diet and physical activity will be discussed (See Action Plan, *Progress Note Form for CHW Intervention*). In addition to phone calls, CHWs will also contact patients via a secure NYULMC phone through text messages to communicate study activities(see Text Message Script). CHWs will also work with partner agencies to conduct community-level activities, such as culturally tailored physical fitness classes and healthy cooking demonstrations, that patients will be invited to attend. The CHWs will make necessary referrals to other services available in the community (i.e. exercise classes, social services, mental health, tobacco cessation, etc.). CHWs will complete an *Encounter Report* to document unscheduled encounters with study participants (ie. such as when a participant calls the CHW to request referrals to services or to report an illness or new diagnosis.) In order to understand the COVID-related impact and needs of study participants in managing their health and to improve CHW referrals during the COVID19 pandemic, CHWs will complete a Rapid COVID Assessment via phone up to once per month or as needed (see study forms for: *Rapid COVID Assessment*, *Rapid COVID Assessment – Repeating Form*).

Multiple sessions will be hosted at varying times/days of the week to accommodate schedules of both working individuals and at-home caretakers. Small incentives will be provided throughout the intervention to encourage ongoing attendance, and incentives will be distributed at program completion for individuals who attended all 5 sessions.

#### Consenting and data collection with waitlisted control participants

For control participants, the study will collect EHR data on clinical measures only that will be linked to a unique identifier housed at the primary care practices; there will be no survey data collection with control participants. In other words, the study will not be evaluating changes in study outcomes via non-EHR data among waitlisted control participants who receive the CHW intervention. For these reasons, we are requesting a waiver of authorization (see *Section IVb Process of Consent*). After completion of Round 1 intervention with intervention participants, CHWs will call contact waitlisted control participants regarding the group education sessions. Control participants will be offered the same content and dosage of education sessions.

#### C4. Provider Survey

At baseline and follow-up, brief surveys will be administered to all participating physicians (n=80) by the NYU study team to capture data on: satisfaction with workflow before and after intervention, information

sources for EHR-CHW initiatives before and after intervention, acceptability of and satisfaction with the integrated EHR-CHW intervention, and barriers and facilitators of point-of-care use of the tools (See *Provider Survey and Provider Survey – Follow-up*). The follow up provider survey will also include additional variables of organizational climate and priority and effects of the COVID-19 pandemic at the individual practices (eg. including questions to assess impact of COVID-19 on the practice and if providers are providing and/or tracking COVID-19 vaccination among patients in order to inform tailoring of remote intervention to support vaccination efforts and assist follow-up by CHWs to encourage vaccination among patients with overweight and pre-diabetes who are at higher risk for complications from COVID-19)

Survey items with response scales will be designed to capture data on each of the research questions. For instance, participants may be asked to respond on a five-point scale from strongly agree to strongly disagree to the following statements: “Pre-diabetes testing recommendations are useful to me in my practice”, or “The HbA1c testing alerts in the EHR are helpful to me”, or to indicate how frequently they use each in a set of common information sources for clinical decision support. Provider Surveys will be administered via online survey software or paper copy if requested. Surveys will take approximately 15 minutes to complete.

#### C5. Key Informant Interviews

Qualitative key informant interviews will be conducted with physician champions at each site and/or administrator of each site, Healthfirst representatives, community advisory board members, study staff, and CHWs (n=100) (See *Key Informant Interview Guide*). At baseline, the interviews will be incorporated into the workflow analysis to assess current satisfaction and usage of EHR and health coaching. At follow-up, the interviews will assess barriers and facilitators to the implementation and adoption process of the integrated EHR-CHW intervention, fidelity to the interventions, and to solicit recommendations for the replication and scalability of the intervention to other sites and insurer organizations. Follow-up interviews completed during the pandemic will assess impact of COVID-19 on the practice, attitudes towards the remote CHW intervention adapted for their patients during the pandemic, and if providers are providing and/or tracking COVID-19 vaccination among patients. These questions are intended to assess satisfaction with the remote intervention and inform strategies to support vaccination efforts and assist follow-up by CHWs to encourage vaccination among patients with overweight and pre-diabetes who are at higher risk for complications from COVID-19 (See *Key Informant Interview Guide - provider – remote intervention*). A member of the NYU study team will conduct the interviews. Questions will be adapted from existing validated measures on acceptability, feasibility, adoption, organizational culture, and scalability. What organizational barriers and facilitators appear to influence implementation and how? Did members of the practice understand and respect the respective roles of physicians, CHWs, and other members of the team? How did this organization customize the intervention to better serve its own local needs? How were users involved in design and implementation? What are recommendations for replicating this model for other clinical settings and communities? Do project findings motivate payer organizations to reimburse CHW services? Key Informant Interviews will take approximately 30 minutes to complete.

## **II. CHARACTERISTICS OF THE RESEARCH POPULATION**

The overall number of subjects expected to participate in this study is 1220.

This includes a total of 1040 participants in the EHR-CHW Intervention, 80 subjects who participate in the surveys and 100 participants in the key informant interviews.

#### *CHW Intervention*

Inclusion Criteria: Participants will be eligible for study participation if they meet the following criteria: a) self identify as South Asian; b) are at least 21 years of age and younger than age 75, c) had an appointment with a physician or mid-level clinician for routine non-emergent primary care in the last 12

Protocol: s17-00693

Version Date 9.28.21

months; d) have a BMI of  $\geq 23$ ; and e) have incident pre-diabetes as determined by HbA1c test (last A1c test date in the last 12 months).

Exclusion Criteria: Patients under the age of 21 and older than 75 will be excluded. Individuals with a diagnosis of diabetes or pre-diabetes during the 12 months prior to intervention implementation will be excluded. Pregnant women and all visits with an obstetrician gynecologist are excluded.

No children or vulnerable subjects will be enrolled in this study.

#### *Provider Assessment Surveys*

The inclusion criteria for the surveys are as follows: adult (18 years and over); clinicians employed by independent primary care practice that are members of HealthFirst's network and have enrolled into the study.

Exclusion criteria include the following: participants who are unable to complete the survey in the English language.

#### *Key Informant Interviews*

The inclusion criteria for the interviews are as follows: adult (18 years and over); must be a provider, clinic manager, Healthfisrt staff, community advisory board member, study staff, or community health worker. Exclusion criteria include the following: participants who are unable to participate in the interview conducted in the English language.

### **III. METHODS and PROCEDURES**

#### **A. Methods and Procedures**

##### A1. Integrated EHR-CHW Intervention

###### *PCP Enrollment*

Practices that express interest in participating in the intervention will sign a Memorandum of Understanding (MOU) that outlines the nature of the evaluation and the uses of any data collected, including:

- i. Training requirements
- ii. CHW intervention components to be implemented
- iii. Individual-level participant data to be extracted routinely from EHR and provided to study team
- iv. Confidentiality and data storage procedures

All relevant parties will then sign the MOU.

###### *Intervention Components*

A minimum set of proposed intervention components will be implemented at all participating practices, including:

- An alert to identify South Asian patients with elevated BMI ( $\geq 23 \text{ kg/m}^2$ ) and recommendation to order an HbA1c test
- Generation of registry lists of individuals with A1C 5.7-6.4% (individuals with incident pre-diabetes).
- 5 group-based health education sessions on diabetes prevention
- Provision of culturally and linguistically tailored health information and resources
- Up to 9 follow-up calls/meetings to engage in goal-setting activities regarding changes to health behaviors, medication adherence, or other issues related to diabetes prevention as identified jointly by patient and CHW.
- Participants will develop with the CHW and receive a copy of their long-term and short-term Participant Action Plan.
- Referrals to other services available in the community (i.e. exercise classes, social services, mental health, tobacco cessation, etc.

- EHR-CHW integration supporting team-based care and feedback between PCPs and CHWs within the clinic, including:
  - First, providers will be sent Enrollment Update Letters during the recruitment phase of the intervention regarding the status of enrollment at their site (see Provider Enrollment Update Letter). This document will be sent as a password protected file with the password sent in a separate file from the enrollment status.
  - Second, templates will be created that CHWs can complete and upload into the EHR. Providers will be able to access these templates which will include the following: 1) CHW action planning documents and individualized counseling conducted during protocolized phone calls; and 2) Patient progress in reaching goals related to weight loss and behavior change.
  - Third, health coaching and referral materials will be made available to providers through the EHR, including 1) Culturally adapted CHW curriculum materials; and 2) Systems to link patient to community resources and activities.
  - Fourth, CHW communication with the healthcare team will be facilitated by participation and report-backs from CHWs during regular team “huddles” or staff meetings at least once per month. Further frequency of participation will be site-specific and guided by input from the provider and workflow analysis findings in order to avoid provider burn-out.

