## C. Study Design

### C1. Overall Design/Site Selection/Site Enrollment

We will use a randomized controlled trial design with staggered-entry and a waitlist controlled group to compare the effectiveness of an alert and registry-driven CHW-led coaching compared with usual care among patients with BMI at baseline of  $\geq 23 \text{ kg/m}^2$ . Randomization will be at the individual-level and stratified by PCP, meaning eligible intervention and control participants will be randomized for each PCP. PCPs will be clustered into waves, aligning with the original stepped-wedge design. Entry into the study will be staggered in three waves, with each wave consisting of six to seven PCPs (See Figure 1). All 20 PCPs will be recruited and enrolled by month 6 of Year 2 (study period 6, Figure 1), and we will assign 6-7 practices into each of the 3 waves upon enrollment. For each PCP, there will be a total of two rounds of consecutive six-month CHW intervention periods: 1 month for recruitment and enrollment of intervention participants and five months of community health worker-led group education sessions (approximately one session per month). Data related to the study outcomes will be extracted from EHR systems a total three times (baseline, 6 month, and 12 month) for each PCP. Randomization at each PCP will occur during the first round. Prior to allocation into treatment group, each treatment participant will be matched to a control participant based on age, gender, and BMI. Intervention participants will be split into two groups and assigned to either first or second round. All control participants will be waitlisted during the first round and will be offered the full CHW group education sessions during the second round. PCPs will be placed into waves based on geographic location and CHW caseload considerations. PCPs will be eligible for participation if they have a) an overall patient volume of  $N \geq 1000$ ; b) at least 70% of the patient population is South Asian; and c) the practice has used EHR for at least 12 months. All PCPs will sign a Memorandum of Understanding (MOU) between the PCP and NYU outlining study commitments.

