**4. Cost-Effectiveness/Sustainability:** What were the costs of the integrated intervention to the insurer organizations and physician practice and did these additional costs provide added value at patient and provider levels? What were the net costs and benefits of different combinations of CHW and EHR interventions?

Using average resource utilization and costs per patient (in first 6 and 12 months of follow-up), we will compare resources incurred by the trial arms during the follow-up period at each time point. Our outcome will be the incremental cost per person achieving 5% weight loss. Cost data will be used to inform HF leadership of program costs for consideration of sustainability of CHW models by payer organizations.

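### The planned cost per 5% weight-loss success prices CHW coaching added to EHR tools that both arms share, not the integrated package, and only one EHR/CHW combination can be contrasted

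*Combined protocol and SAP*

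**What the plan says.** Section C1 (Overall Design) fixes the unit of randomisation: "Randomization will be at the individual-level and stratified by PCP, meaning eligible intervention and control participants will be randomized for each PCP". The CHW Component section gives the order of events: "Patients that meet eligibility criteria will be drawn from registry lists and randomized to intervention or waitlisted control". Section VI.A repeats this.

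The EHR side is defined at practice level in section C2: "The EHR component of the integrated EHR-CHW intervention will include: 1) An alert to identify South Asian patients with elevated BMI", together with registry lists of patients in the pre-diabetes HbA1c range. C2 adds a workflow analysis at each practice. Its training paragraph says that "clinicians will receive an estimated 8 hours of didactic and interactive training". Section III.A1 (Intervention Components) covers every site: "A minimum set of proposed intervention components will be implemented at all participating practices, including" the alert, the registry, the group sessions, the calls and the EHR-CHW integration. One integration item serves coached patients: "templates will be created that CHWs can complete and upload into the EHR".

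Section III.B2, item 4 (Cost-Effectiveness/Sustainability) asks what the integrated intervention cost the insurer and the practices. It then asks: "What were the net costs and benefits of different combinations of CHW and EHR interventions"? The stated analysis compares average resource use and cost per patient between the arms over the first 6 and 12 months of follow-up, and concludes: "Our outcome will be the incremental cost per person achieving 5% weight loss". Cost data then go to the insurer's leadership to inform decisions about sustainability.

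**The concern.** Item 4 asks about the integrated EHR-CHW intervention, but its only analysis is a difference between two arms that both have the EHR component. A cost that both arms carry equally does not appear in the difference. The control condition is called usual care in Aim 1, yet it is care with the alert, registry and trained clinicians and with coaching deferred.

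The insurer is the intended user of this result. If the ratio is presented without a label, it may be taken as the cost-effectiveness of the whole package, although it describes adding coaching where the EHR tools are already installed and paid for. The combinations question has a related problem: the design supplies two of the four possible EHR-by-CHW conditions, so most of what the question asks has no data behind it.

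**Working it through.** **Inputs.** The documents state no cost figure, so there is none to reproduce. The numerical input is the 8-point difference in the Power Calculation (III.B1), with 1040 patients randomised 1:1 (520 per arm). The plan's power statement bears on this point only through that denominator. With 520 × 0.85 = 442 analysed per arm, power is 0.930 for 10% vs 18% and 0.796 for 20% vs 28%. The stated figure above 80% therefore holds if the control rate, which is not given, is about 19.6% or lower.

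**Step 1: which costs each arm carries.**

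| Item | Where stated | Control | Intervention |
|---|---|---|---|
| Alert, registry | C2; III.A1 | yes | yes |
| Workflow analysis, clinician training | C2 | yes (same practices and clinicians) | yes |
| Alert-prompted HbA1c before registry entry | C2; CHW Component | yes | yes |
| CHW sessions and calls | III.A1 | deferred | yes |
| CHW templates uploaded to the EHR, CHW report-backs | III.A1 | deferred | yes |

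**Step 2: the ratio.** Per patient, let E be the shared EHR cost (first three rows), H the CHW cost and L the CHW-specific EHR linkage cost. With equal charging of E to both arms:

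(E + H + L − E) / 0.08 = (H + L) / 0.08 = 12.5 × (H + L).

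E drops out; L stays in. Set-up, training and the qualifying HbA1c test may also fall before the follow-up window, which would remove them in any case.

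**Step 3: range.** The size of E is not given. Take total cost per intervention patient as 100 units and assume a share for E:

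| Assumed share of E | Arm-based ratio | Ratio with E charged to the intervention, same 0.08 |
|---|---|---|
| 10% | 90/0.08 = 1125 | 1250 |
| 25% | 75/0.08 = 937.5 | 1250 |
| 50% | 50/0.08 = 625 | 1250 |
| 75% | 25/0.08 = 312.5 | 1250 |

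The arm-based ratio is lower by exactly the assumed share. The last column reuses 0.08 for a comparison that the trial does not make, so it is illustrative only.

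**Step 4: direction for a payer without the tools.** Let d be the unobserved effect of the EHR tools alone. That payer's ratio is (E + H + L)/(0.08 + d). It exceeds (H + L)/0.08 only if d < 0.08 × E/(H + L). For E at 10%, 25%, 50% and 75% of the total, the break-even d is 8 × 10/90 = 0.9, 8 × 25/75 = 2.7, 8 × 50/50 = 8 and 8 × 75/25 = 24 percentage points. Neither E nor d is known, so the direction is undetermined.

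**Step 5: combinations.** With columns (intercept, EHR, CHW, EHR×CHW), the observed rows are control (1,1,0,0) and intervention (1,1,1,1), of rank 2 for 4 parameters. Their difference (0,0,1,1), the CHW effect given EHR, is estimable. The EHR effect, the CHW effect without EHR and the interaction are not. The pre/post comparisons in Aim 2 concern quality-measurement reports and provider attitudes, not cost or weight.

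**Step 6: data in both arms.** III.A2 lists insurer claims among the data, but section VI.G (Control Participants) says that no claims data are collected for controls. Section C1 and the section on waitlisted controls offer them the same sessions after round 1, so a 12-month comparison includes coached controls.

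**The case against.** Shared costs drop out of any incremental ratio, and the sentence listing components at all practices contains no error. Item 4 also intends to inform the insurer of programme costs, so the ratio is not all that the insurer would receive. This is one question within Aim 2 and leaves the primary comparison untouched. All of that stands. It limits the point to what the ratio is called and what accompanies it.

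Some stronger readings are tempting, but the documents do not support them:

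- A reader might infer that every EHR-related cost cancels. CHW templates and report-backs serve coached patients, so their cost stays in the increment.
- A reader might infer that cancellation holds under any costing method. Item 4 gives no allocation rule, and cancellation follows only if shared costs are charged equally to both arms.
- A reader might infer that the combinations question has no contrast at all. EHR alone versus EHR plus CHW is one such contrast and is estimable.
- A reader might infer that a payer starting without the tools would certainly face a higher cost per success. Step 4 shows that this depends on an EHR effect that the trial does not observe.

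In the other direction, the Purpose section still refers to a stepped-wedge design, which might seem to supply periods without EHR tools. C1 sets out individual randomisation within practice. Even a stepped rollout of the whole package would give no separate EHR-only or CHW-only condition.

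**Conclusion.** The point holds in this form. As written, item 4 yields the incremental cost of CHW coaching and its CHW-specific EHR linkage, given EHR tools already in place. It does not yield the cost-effectiveness of the integrated package against care without it, and it answers only one part of the combinations question. CHW without EHR, and neither component, are never observed.

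At an 8-point difference, the ratio falls by 12.5 units for each unit of shared cost per patient left out. The overall size cannot be stated without cost data. The conclusion assumes ordinary arm-level costing and the individually randomised design of C1. It should be corrected because the result is meant for a payer's decision. The primary efficacy analysis is unaffected.

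**What to change.** In section III.B2, item 4:

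1. Replace the combinations question with one on the incremental cost and effect of adding CHW coaching to the EHR alert and registry.
2. Label the ratio as that add-on contrast, state how shared costs are allocated, and do not present the ratio as the cost-effectiveness of the integrated intervention.
3. Report shared EHR costs (set-up, workflow analysis, training, alert-prompted HbA1c tests) separately as descriptive programme cost per practice and per registry patient, alongside the ratio. III.A2 lists no set-up or training cost items, so a source for them must be named.
4. Limit the between-arm comparison to resources measured in both arms, since controls have no claims data. Treat the 6-month ratio as the main one, because controls are offered coaching after round 1. C1 also places part of the intervention arm in round 2, so state which round's six months the ratio uses.

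The cost is a rewording of one item, one extra descriptive table and some record-keeping. The downside is a narrower cost claim. No new patients and no change of design are needed.
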